2.5.3. Vital Signs

Changes from Baseline in vital signs parameters (systolic and diastolic blood pressures, pulse rate) will be summarized at each evaluation. All vital signs data will be shown in subject data listings.

2.5.4. Physical Examination and EKG

Physical examinations (HEENT, lungs, heart, abdomen, skin, and neurologic) will be performed for all subjects at Baseline (Visit 2) and Week 12 (Visit 5). EKGs will be performed for all subjects at Baseline (Visit 2), Week 4 (Visit 3), and Week 12 (Visit 5). Results will be presented in subject data listings.

2.5.5. Safety Laboratory Values

Hematology/chemistry/urinalysis safety laboratory parameters will be performed for all subjects at Baseline (Visit 2), Week 4 (Visit 3), and Week 12 (Visit 5). Summary tables for the individual laboratory parameters will be presented showing observed value and change from baseline. Laboratory test results will be shown in subject data listings.

Urine pregnancy tests will be performed at all visits for female subjects of child bearing potential, and will be presented in subject data listings.

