## 7.6 Early Withdrawal of Subjects

1. Subjects should be withdrawn from the study if they no longer wish to participate, are being uncooperative, or if the Investigator feels that it is in the best interest of the subject to withdraw.
2. Subjects with protocol deviations or for whom it is discovered should have been excluded should not be withdrawn unless there is a safety concern. The protocol deviation should be recorded in the subject's source documents and the eCRF.
3. If during the course of treatment a subject experiences a cardiovascular or hematologic AE (including abnormal laboratory values) of Common Terminology Criteria for Adverse Events (CTCAE) Version 4.02 Grade 2 or higher, the study product will be discontinued and the subject will be withdrawn from the study.
4. Subjects who experience an AE resulting in or requiring discontinuation of study product use should be encouraged to be followed until the AE is resolved or stabilized.
5. If a female subject becomes pregnant during the study, study product will be discontinued immediately and she will be followed through the pregnancy and delivery. Details of the pregnancy, delivery and health of the infant should be recorded on the Pregnancy Surveillance Form. The Sponsor will be notified immediately after the subject is detected to be pregnant.
6. At the time of study discontinuation, the Investigator will record the reason for early withdrawal, date of last study product application, date of last visit or contact, collect adverse event data, and, if possible, perform all End of Study Visit specific evaluations. Every attempt should be made to contact subjects who are lost-to-follow-up. At least three attempts must be documented in the subject's source document, including the use of at least one certified letter. Any contact, either direct or indirect, should be made with the purpose to document the final status of the subject with regard to safety. Subjects who withdraw early will not be replaced.

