#### **7.10.7 Early Withdrawal**

If a subject is withdrawn from the study according to any of the criteria defined in Section 7.6, the following procedures will be performed:

1. Evaluate treatment and protocol compliance and record any deviations. This includes a review of the diary card for number of applications and missed applications.
2. Investigator is to document the number and location of the lesions with in the treatment area and on a grid foil. One copy of the grid foil should be inserted into the subject's source document.
3. Collect vital signs (blood pressure and pulse rate).
4. Perform a physical examination (HEENT, lungs, heart, abdomen, skin, and neurologic).
5. Perform a 12-lead EKG.
6. Collect blood (2/3 tablespoon) and urine for hematology/chemistry/urinalysis safety labs.
7. Conduct a urine pregnancy test for all females of child bearing potential.
8. Collect AE data. This includes a review of the diary card for potential AEs.
9. Update concomitant medications data.
10. Weigh tubes when they are collected.
11. Complete eCRF.

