## 11.2 Analysis Data Set

### 11.2.1 Intent to Treat

The intent-to-treat population (ITT) will be the primary efficacy analysis data set and consists of all subjects who are randomized and dispensed study medication.

Missing data for efficacy analysis will be replaced using last observation carried forward (LOCF). If a subject withdraws early from the study, that subject's efficacy assessments captured at the early termination visit will be assigned to the nearest corresponding scheduled visit that has been missed.

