2.10. Handling Missing Data

Listings will be provided for all data. Descriptive statistics will be provided for all planned visits as provided on the eCRFs. No imputations for missing data will be used in the data displayed in the listings such that the listing will only show “observed data”.

Dates related to the adverse events and medications will be imputed using the rules below in an effort to categorize them properly into the summary tables.

Imputing partial or missing start dates:

- If the year is unknown, then the start date will not be imputed. The date will remain missing.
- If the month is unknown and the year is the same as the first administration of study product date of the study, then impute the month and day of the date to be equal to the first administration of study product month and day. Otherwise, impute the month as January.
- If the day is unknown and the month and year are the same as the first administration of study product date of the study, then impute the day to be equal to the day of the first administration of study product. Otherwise, impute the day as ‘01’.

Impute partial or missing stop dates:

- If the year is unknown, then the stop date will not be imputed. The date will remain missing.

- If the month is unknown, impute the month as December.
- If the day is unknown, impute the day to be the last day of the month.

If an imputed stop date is greater than the date of study completion/discontinuation date of the study, then the imputed stop date will be set equal to the date of completion/discontinuation date.

The imputed dates will be stored in the analysis datasets along with the original dates as recorded by the sites.

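### Labs drawn at early withdrawal have no stated summary, and the Week 12 hematology table loses subjects withdrawn earlier for Grade 2 or higher hematologic abnormality

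*SAP*

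**What the plan says.** **Who leaves, and what is collected.** Protocol 7.6 item 3 covers any subject who, during treatment, has a cardiovascular or hematologic adverse event of CTCAE Grade 2 or higher, with abnormal laboratory values counted. For that subject "the study product will be discontinued and the subject will be withdrawn from the study". The early-withdrawal procedures in Protocol 7.10.7 include the step "Collect blood (2/3 tablespoon) and urine for hematology/chemistry/urinalysis safety labs".

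**What is summarised.** SAP 2.5.5 names laboratory draws at Baseline, Week 4 and Week 12, and then says: "Summary tables for the individual laboratory parameters will be presented showing observed value and change from baseline". It adds: "Laboratory test results will be shown in subject data listings". SAP 2.10 says: "Descriptive statistics will be provided for all planned visits as provided on the eCRFs". SAP 2.2 rules out imputation of missing safety data.

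**Where early-termination data go.** The only mapping rule is in Protocol 11.2.1, and it is limited to efficacy: "that subject's efficacy assessments captured at the early termination visit will be assigned to the nearest corresponding scheduled visit". The table list in SAP 4.1 has one summary per laboratory panel (Tables 14.3.2.1 to 14.3.2.3). It names no shift table, no worst-value table and no early-withdrawal row. SAP 4.3 places the table shells in a separate file, which is not among the documents.

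**The concern.** Subjects withdrawn under item 3 before Week 12 have no Week 12 draw. For hematology this missingness is informative by rule, because the value itself can be what removes the subject. A Grade 2 result at the Week 4 draw counts in the Week 4 summary, and then that subject is absent at Week 12. The change from Week 4 to Week 12 can therefore look more favourable than it was, and more so in an arm with more such withdrawals. The blood drawn at the withdrawal visit, or at any unscheduled visit, has no summary assigned to it in the text.

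This matters because the study objective includes the dose-response of safety, so laboratory tables will be compared across the four arms. There is no data safety monitoring board (Protocol 7.9) and no interim analysis (SAP 2.7), so the final tables are the planned by-arm view of these values. EKG results are listed only (SAP 2.5.4).

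**Working it through.** **Step 1: follow the data through the text.**

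- *Grade 2 value first seen at the Week 4 draw.* It is in the Week 4 summary. The subject is then withdrawn and has no Week 12 value. The repeat draw at withdrawal has no stated summary.
- *Abnormality first found between Weeks 4 and 12.* No draw is scheduled for 12 − 4 = 8 weeks, or 8/12 = 67% of treatment. If a clinical event or an unscheduled draw reveals it, the withdrawal or unscheduled result may be the only one that shows it, and no summary is named for that result.
- *Grade 2 value first seen at the Week 12 draw.* It is in the Week 12 summary, and nothing is lost.

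**Step 2: inputs for the size.** The documents give no rate of Grade 2 or higher hematologic events, so there is no planned figure to reproduce for this point. The one planned figure used is the arm size: 54/(1 − 0.10) = 60 (SAP 2.8). Assumptions:

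- a fraction q of an arm is withdrawn under item 3 before Week 12
- those subjects are the worst tail of one normally distributed parameter
- the triggering value and the Week 12 value have correlation r between 0.5 and 0.9

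**Step 3: formulas.** Let z be the q-quantile of the standard normal and φ its density.

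- Expected number withdrawn per arm: 60q
- Chance of at least one in an arm: 1 − (1 − q)^60
- Mean distance of the removed subjects from the centre on the triggering value: φ(z)/q
- Shift in the Week 12 mean of those remaining: r × φ(z)/(1 − q)

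**Step 4: results.**

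| q | Expected per arm | Chance of at least one | Mean distance of removed (SD) | φ(z)/(1 − q) | Shift for r = 0.5 to 0.9 (SD) |
|---|---|---|---|---|---|
| 1% | 0.6 | 45% | 2.7 | 0.027 | 0.01 to 0.02 |
| 2% | 1.2 | 70% | 2.4 | 0.049 | 0.02 to 0.04 |
| 5% | 3 | 95% | 2.1 | 0.109 | 0.05 to 0.10 |
| 10% | 6 | more than 99% | 1.8 | 0.195 | 0.10 to 0.18 |

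For example, at 2% the shift runs from 0.5 × 0.049 = 0.025 to 0.9 × 0.049 = 0.044.

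**Step 5: scale.** The standard error of an arm mean is 1/√60 = 0.13 SD. The shifts at 2% and 5% are below one standard error. The 10% row is an outer bound, since it would spend the whole planned all-cause drop-out of 10% on one tail of one parameter. The subjects removed, however, lie about 2 SD or more from the centre at 1% to 5%, and those are the values a safety table is meant to show.

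**Step 6: a related mismatch.** Protocol 7.6 item 6 asks, where possible, for the End of Study Visit evaluations at discontinuation. That visit has no laboratory draw in the Study Schedule or in Protocol 7.10.6. Protocol 7.10.7 requires laboratory draws at early withdrawal. The two passages do not agree on whether a withdrawal sample is taken.

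**The case against.** The strongest reply is that little is lost. On-treatment draws are scheduled only at Weeks 4 and 12, so a withdrawal triggered by a laboratory value will normally come from one of them, and that value stays in its own visit's summary. SAP 2.1 gives N, minimum and maximum, so both the extreme and the fall in N are visible. A qualifying abnormality is an adverse event, so it is counted by arm in the treatment-emergent tables and in Table 14.3.1.4. No laboratory hypothesis test is planned, and observed-case summaries without imputation are common.

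All of that stands, and it rules out several stronger readings that a reader might infer:

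- *That the laboratory tables omit the worst values as a matter of design.* They do not. What is missing is the withdrawal or unscheduled draw and the later Week 12 value.
- *That the withdrawal sample is often the only one showing the event.* The 8-week gap does not establish that. With no draw, an abnormality without symptoms would usually go unseen.
- *That chemistry and urinalysis are selected in the same way.* Item 3 names cardiovascular and hematologic events only.
- *That vital signs share the problem.* SAP 2.5.3 summarises them at every evaluation, and early withdrawal includes a vital-sign measurement.
- *That withdrawal results certainly appear only in listings.* SAP 2.5.5 and the laboratory table titles do not say that the tables are by visit, SAP 2.10 depends on how the eCRF defines visits, and the shells are unseen.

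The reply does not answer two things. Counts of events do not show how far values moved from baseline, and the Week 12 hematology summary remains conditional on not having been withdrawn earlier for hematology.

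**Conclusion.** The point holds in a limited form. The SAP text gives early-withdrawal and unscheduled laboratory results no summary, and the Week 12 hematology summary excludes subjects withdrawn earlier under item 3 for a reason tied to the value itself.

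The effect on means is small: about 0.02 to 0.04 SD at an assumed 2% withdrawn and 0.05 to 0.10 SD at 5%. The main loss is in the extremes and in reading Week 4 against Week 12 across arms. These figures rest on assumed withdrawal rates, normality, one-tail removal and r between 0.5 and 0.9. The statement that results may reach only the listings rests on the text without the table shells. Efficacy conclusions are not affected. This is a cheap improvement to the safety reporting and worth making before database lock.

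**What to change.** In SAP 2.5.5:

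- Add a by-arm table of shift from baseline (low, normal, high) or of the worst post-baseline value, at least for hematology. It should use every post-baseline result, including early-withdrawal and unscheduled draws.
- Footnote the Week 12 hematology table with the number per arm withdrawn under Protocol 7.6 item 3 before that visit.

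Separately, the sponsor should reconcile Protocol 7.6 item 6 with 7.10.7 on which evaluations are done at discontinuation, since the new table depends on whether that sample exists.

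The tables need a little extra programming. They use data that 7.10.7 already calls for and add no procedures, and sample size and power do not change.

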2.6. Efficacy

Primary endpoint

For statistical assessment of the primary endpoint with a significance level of 0.05 the following underlying hypotheses are used:

$H_0: p_1 \leq p_2$ vs. $H_a: p_1 > p_2$

Where p_1 is the treatment effect of 2.5% DFD-07 (celecoxib) Cream twice daily and p_2 is the treatment effect of the Vehicle Cream preparation.

Secondary endpoints

For statistical assessment of all product comparisons after certain period of treatment (i.e. at Visits 3, 4, 5 and 6) with a significance level of 0.05, the following underlying hypotheses are used:

$H_0: p_1 \leq p_2$ vs. $H_a: p_1 > p_2$

Where p_1 is the treatment effect of 1.25% or 2.5% DFD-07 (celecoxib) Cream once daily and p_2 is the treatment effect of the Vehicle Cream preparation.

For the percent change from baseline in AK lesion counts, the Mann-Whitney U-test (Wilcoxon rank sum test) will be used to test for treatment differences compared to the Vehicle Cream preparation at a significance level of 0.05.

2.7. Interim Analyses and Database Lock

There are no planned interim analyses for this study.

2.7.1. Database Lock / Final Analysis

The final analysis will take place after database lock. The final analysis will unblind the subjects and contain all the outputs indicated in the table on contents.

2.8. Sample Size and Power Considerations

The sample size estimation of this trial is based on the assumption that the Active product exhibits a complete clearance of the AK lesions in 45% of the subjects, while the Vehicle does so in 20% of the subjects (a difference of 25% between active and Vehicle treatment groups). Assuming a power of 80% and α of 0.05, in order to demonstrate the statistical significance of such an effect difference, 54 patients per treatment group would be needed.

Considering the exploratory dose-response character of the trial, and assuming a drop-out rate of 10%, 60 subjects need to be recruited in each treatment group. With 4 treatment groups in the study, it is planned to recruit approximately 240 subjects in the study.

2.9. Randomization Scheme and Codes

The details related to the randomization is documented in a separate Randomization Plan.

2.10. Handling Missing Data

Listings will be provided for all data. Descriptive statistics will be provided for all planned visits as provided on the eCRFs. No imputations for missing data will be used in the data displayed in the listings such that the listing will only show “observed data”.

Dates related to the adverse events and medications will be imputed using the rules below in an effort to categorize them properly into the summary tables.

Imputing partial or missing start dates:

- If the year is unknown, then the start date will not be imputed. The date will remain missing.
- If the month is unknown and the year is the same as the first administration of study product date of the study, then impute the month and day of the date to be equal to the first administration of study product month and day. Otherwise, impute the month as January.
- If the day is unknown and the month and year are the same as the first administration of study product date of the study, then impute the day to be equal to the day of the first administration of study product. Otherwise, impute the day as ‘01’.

Impute partial or missing stop dates:

- If the year is unknown, then the stop date will not be imputed. The date will remain missing.

- If the month is unknown, impute the month as December.
- If the day is unknown, impute the day to be the last day of the month.

If an imputed stop date is greater than the date of study completion/discontinuation date of the study, then the imputed stop date will be set equal to the date of completion/discontinuation date.

The imputed dates will be stored in the analysis datasets along with the original dates as recorded by the sites.

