## 7 STUDY PROCEDURES AND EVALUATIONS

### 7.1 Screening

A separate Screening Visit (Visit 1) may be performed when a washout period is required or for scheduling purposes. Alternatively, Visits 1 (Screening) and 2 (Baseline/Day 1) may be combined if no washout period is required. The subject number, date of visit, date of informed consent, reason for screen failure (if applicable) and study status will be captured in the eCRF for every screen failure subject. The Baseline/Day 1 (Visit 2) Visit must occur no later than 60 days after the Screening Visit. Medical history should be collected for the prior 1 year period and concomitant medications, therapies, and procedures collected for the prior 6-month period. Only ongoing medical conditions and ongoing concomitant medications should be entered into the eCRF.

A screen failure is a subject who received information about the study, including signing an informed consent and possibly performing some study-related procedures, but was not randomized and/or did not use study product.

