2.4.3. Prior and Concomitant Medications

Prior and concomitant medications will be summarized by frequencies and percentages. All medications will be coded using the World Health Organization (WHO) Drug dictionary September 2016 version.

Prior medications will be defined as any medication that started prior to the first day of injection. Concomitant medications will be defined as any medication that starts or is ongoing on or after the first day of injection. A medication may qualify as both a prior and concomitant medication if it started prior to first dose and is ongoing or stopped after the day of dosing.

Medications will be summarized by treatment.

Section 2.10 describes the imputation rules for partial dates. All medications will be presented in a data listing.

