2.5.1. Adverse Events (AEs)

Adverse events will be coded using the medical dictionary of regulatory activities (MedDRA Version 19.1) dictionary.

All reported treatment emergent AEs will be summarized by treatment group, the number of subjects reporting events and the no. of AEs reported, system organ class, preferred term, severity, relationship to study product, and seriousness. When summarizing AEs by causality and severity, each subject will be counted only once within a system organ class or preferred term by using the event with the greatest relationship and highest severity within each classification.

Serious adverse events (SAEs) will be summarized by severity and relationship to study product, and SAEs will be listed by subject. In addition, a list of subjects who prematurely discontinued from the study due to an AE will be provided.

All information pertaining to AEs noted during the study will be listed by subject, detailing verbatim term given by the Investigator, preferred term, system organ class, onset date, resolution date, maximum severity, seriousness, action taken regarding study product, corrective treatment, outcome and drug relatedness. The event onset will also be shown relative (in number of days) to date of first administration.

AEs related to study procedures done before study product administration will be provided in a data listing.

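### SAP 2.10 sets certain partial start dates to the first-dose date without checking them against a known stop date or an earlier Screening record, so some pre-dose records are misclassified

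*SAP*

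**What the plan says.** SAP 2.10 states that the rules serve to place records in the right tables: "Dates related to the adverse events and medications will be imputed using the rules below in an effort to categorize them properly into the summary". The start-date rules are:

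- Year unknown: "If the year is unknown, then the start date will not be imputed. The date will remain missing".
- Month unknown, year equal to the first-dose year: "then impute the month and day of the date to be equal to the first administration of study product month and day". For any other year the month becomes January.
- Day unknown, month and year equal to those of first dose: "then impute the day to be equal to the day of the first administration of study product". Otherwise the day becomes 01.

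The only consistency limit concerns stop dates. It begins "If an imputed stop date is greater than the date of study completion/discontinuation date of the study" and resets such a date to the completion or discontinuation date. Imputed start dates have no limit.

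SAP 2.4.3 refers to 2.10 for partial dates. It counts a drug as prior only if it started before the first dosing day. It adds: "Concomitant medications will be defined as any medication that starts or is ongoing on or after the first day of injection". (The product is a cream; I read injection as first application.) The same section lets a drug be both prior and concomitant.

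At Screening, Protocol 7.1 directs: "Only ongoing medical conditions and ongoing concomitant medications should be entered into the eCRF". Screening may precede Day 1 by up to 60 days, or be combined with it when no washout is needed. Protocol 7.10.2 and 8.1 have procedure-related events between Screening and Baseline reported as AEs; other events in that interval go to medical history. The protocol synopsis (Criteria for Evaluation) treats AEs in the treatment period as treatment-emergent. SAP 2.5.1 says: "AEs related to study procedures done before study product administration will be provided in a data listing".

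**The concern.** Placing a truly unknown onset on the first-dose date is a common and cautious convention. The difficulty is that SAP 2.10 applies it even when other fields on the record rule that date out. A stop date before Day 1 shows that the start was before Day 1. An entry as ongoing at a Screening visit held on an earlier day shows the same. The rule consults neither, so it defeats its own stated aim of correct categorization.

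At stake are impossible start and stop pairs in the analysis datasets, an undercount in the prior-medication table, and the chance that an event which ended before any exposure is counted as treatment-emergent.

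**Working it through.** The plan gives no figure to reproduce. The check applies the rule to test records.

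**Inputs.** The start-date rules of SAP 2.10, the definitions of SAP 2.4.3, and the treatment-emergent definition in the protocol synopsis. Illustrative dates (assumptions): Screening 1 August 2016, first dose 20 August 2016. The visits are separate and 19 days apart, within the 60 allowed.

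| Record | Start under SAP 2.10 | Resulting class | Class shown by the record |
|---|---|---|---|
| 1. Drug, year 2016 only, ongoing at Screening | 20 Aug 2016 | concomitant only | prior and concomitant |
| 2. Drug, August 2016, recorded at Screening on 1 August | 20 Aug 2016 | concomitant only | prior and concomitant |
| 3. Drug, July 2016, ongoing | 1 Jul 2016 | prior and concomitant | same |
| 4. Drug, year 2015 only, ongoing | 1 Jan 2015 | prior and concomitant | same |
| 5. Year unknown | missing | not imputed | – |
| 6. Drug, year 2016 only, stopped 10 August 2016 | 20 Aug 2016 | start after stop | prior only |
| 7. Screening-procedure AE, August 2016, stopped 10 August 2016 | 20 Aug 2016 | start after stop; treatment-emergent | pre-dose |

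**Start after stop (records 6 and 7).** 20 August − 10 August = 10 days: each record starts 10 days after it ended. For record 6 the class depends on how SAP 2.4.3 is read. Taken literally, a start on the first dosing day makes the drug concomitant. If the stop date is also consulted, it is neither prior nor concomitant. Both are wrong.

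**Loss of prior status (records 1 and 2).** The imputed start equals the first-dose date, and a prior drug must start before it. Both drugs were in use on 1 August, so the test fails against a fact already in the data. Being ongoing on 20 August, both remain concomitant.

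**Where the rule works (records 3 and 4).** A known earlier month or year is imputed to the first of the month or to January, and the drug stays prior.

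**Width of the window.** Suppose first-dose dates are spread evenly over a 366-day year (assumption). The number of pre-dose days in the same year then averages (0 + 1 + … + 365)/366 = 182.5, with range 0 to 365. The number in the same month averages 14.8, with range 0 to 30. The unknown-month branch is therefore the wider one. These are windows of possible true starts, not counts of affected records.

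**With a cap.** Limit the imputed start to the stop date, or to the Screening date for a drug ongoing at Screening. Records 1 and 2 become 1 August 2016 (prior and concomitant). Record 6 becomes 10 August (prior). Record 7 becomes 10 August (not treatment-emergent).

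**Why a lower limit is also needed for AEs.** Take Screening on 15 July, first dose on 20 August, and a procedure-related AE dated July with the day unknown. The present rule gives 1 July, 14 days before the procedure that caused it. A lower limit at Screening gives 15 July.

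**The case against.** The strongest case for leaving the rule alone is that it is cautious, traceable and of little consequence. Ambiguous onsets go to the treatment period. Original dates are kept beside imputed ones, and listings show observed data only. The Documentation of Statistical Decisions (SAP 2.1) records data issues and their handling before database lock. Eligibility rests on the medication history (Protocol 6.7), and per-protocol exclusions on a blinded review of medication use (SAP 2.2), not on a prior or concomitant label.

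The AE route is also narrow. Only procedure-related events count as AEs before dosing, and the Screening Visit has no blood draw or EKG. The event must have a partial start in the first-dose month or year and a stop before first dose. When the two visits are combined there is no interval at all.

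Most of this stands and keeps the point minor. It does not remove it. Caution about unknown onsets does not justify overriding a recorded stop date. Traceability does not correct the summary tables, and a correction noted at lock is not a pre-specified rule.

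A reader might infer that a misdated AE disappears from Listing 16.2.7.4. The documents do not support that: the listing uses no imputed dates and is defined by relation to pre-dose procedures. The event would appear there and could also be counted in a treatment-emergent table.

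**Conclusion.** The point holds as a minor defect in a stated rule. Start-after-stop pairs follow directly from the text whenever a qualifying partial start date meets a stop date before Day 1. Loss of prior status follows only when Screening and Baseline are on separate days, because a same-day entry does not prove an earlier start.

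A reader might conclude that Table 14.1.4.1 is understated across the board. It is not: only partial dates in the first-dose year or month are affected, and affected ongoing drugs still appear in Table 14.1.4.2.

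Nor can the number of records be estimated from the documents. Assuming 3 to 5 drugs per subject and 2% to 5% qualifying partial dates gives 240 × 3 × 0.02 = 14 to 240 × 5 × 0.05 = 60. Neither factor has a source in the documents, and using all 240 subjects ignores combined visits. That range should not be cited as the size of the problem.

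The consequence is confined to descriptive medication tables and, rarely, an AE count. No efficacy result depends on it.

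**What to change.** Add to SAP 2.10:

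- An imputed start date may not be later than the record's known or imputed stop date.
- For a medication recorded as ongoing at a Screening visit held before Day 1, the imputed start may not be later than the Screening date.
- For a procedure-related AE before first dose, the imputed start may also not be earlier than the Screening date.
- In all other cases the present first-dose rule stays.

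A blanket reset of pre-dose records to 1 January or the first of the month is not advisable, since it could date a procedure-related AE before its procedure.

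The cost is a sentence or two in the SAP and a few lines of code before database lock. No new data are needed.
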